The health care resources consumption will take into consideration the following events related to management of COPD and COPD exacerbations: inpatients and outpatients hospitalization (inward and day-hospital), accesses to emergency room, General Practitioner (GP) and outpatient visits, laboratory tests and examinations, pharmacological (LABA, LAMA, SABA, SAMA, ICS/LABA, steroids, antibiotics, long-Term Oxygen Therapy, etc.) and non-pharmacological therapies (pulmonary rehabilitation) occurred/administered during study period.

Medications for adverse events will be considered too.

The annual direct health care resource consumption and related cost will be provided by means of descriptive statistics of the variables mentioned above. In order to describe the health care cost from enrolment up to the end of 12-month follow-up according to the INHS point of view (26), a two steps approach will be followed: (i) first of all the resource consumed since enrolment will be calculated and then (ii) a monetary value will be assigned to the resource consumption.

(i) Health care resources consumption exclusively related to COPD, COPD exacerbations and COPD-drug-related adverse events will be computed during observational period in terms of pharmacological and non-pharmacological treatments, number of (inward and day-hospital) hospitalizations, number of emergency room accesses, number of GP visits, specialist visits, laboratory tests or examinations (spirometry, FEV1, FVC, FEV1 % of the predicted, RV, IC, TLC, DLCO).

(ii) In order to estimate the economic impact on health care sector related cost (30) of the above mentioned health services (hospital admissions, visits, treatments, examinations, spirometry) consumption, a monetary value to each event recorded will be assigned, as defined by the Italian Ministry of Health through the tariffs in force for outpatient setting (31). The cost of hospitalization will be valued according to the most recent available diagnosis-related group (DRG) tariffs (32); finally, pharmacological treatments will be costed at consumer price. All costs will be expressed in €2015. A monthly (or yearly) cost will be provided by taking into account patients according to duration of observation and parametrizing each patient to the 12-month observation period.

Descriptive statistics (mean, standard deviation, median, minimum and maximum) of the annual direct health care resource consumption and related cost will be provided.

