Non-parametric bootstrap method will be applied to cost data for calculating 95% confidence intervals (22-23).

A multiple linear regression model will be performed to investigate statistical significance of INHS cost predictors (24).

#4 To assess the correlation between patients' satisfaction and resource utilization.

Correlation indexes will be calculated between treatment satisfaction domain scores of TSQM-9 and healthcare resource consumption (such as number of hospitalizations, emergency room accesses, GP visits, laboratory test. etc... during observation period) at 12-month follow-up visit. The patients switching treatment during observation period will not be excluded from analysis and will be evaluated at each visit. The patients stopping treatment during study will be censored at their last available visit.

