4.10 Healthcare resource utilization (secondary objective #3)

Table 20. Hospitalizations not in ICU during observation period: patients' distribution

The table will provide:

- distribution of patients by number of hospitalization not in ICU per patient during observation period (see 'Computed variables' chapter);
- descriptive statistics (mean, median, standard deviation, quartiles, min, max) of number of hospitalization not in ICU during observation period per patient (see 'Computed variables' chapter);
- distribution of patients by "Type of admission" ([F10_RESOURCE_CONS. RES_Hosp_matrix_1__Inw - RES_Hosp_matrix_10__Inw]), considering only hospitalization not in ICU according to the field [RES_Hosp_matrix_x__ICU_YN];
- descriptive statistics (mean, median, standard deviation, quartiles, min, max) of total number of days of hospitalization not in ICU per patient (see 'Computed variables' chapter);
- distribution of patients by reasons for hospitalization not in ICU (i.e. "Hospitalization for" [F10_RESOURCE_CONS. RES_Hosp_matrix_1__hos_for - RES_Hosp_matrix_10__hos_for]).

Descriptives and percentages will be computed out of the total number of FAS patients.

Table 21. Hospitalizations not in ICU during observation period: details

The table will provide:

- distribution of hospitalizations not in ICU by "Type of admission" ([F10_RESOURCE_CONS. RES_Hosp_matrix_1__Inw - RES_Hosp_matrix_10__Inw]), considering only hospitalization not in ICU according to the field [RES_Hosp_matrix_x__ICU_YN];
- distribution of hospitalizations not in ICU by reasons for hospitalization (i.e. "Hospitalization for" [F10_RESOURCE_CONS. RES_Hosp_matrix_1__hos_for - RES_Hosp_matrix_10__hos_for]).

Statistics will be computed out of the total number of hospitalizations not in ICU during observation period in FAS patients.

Table 22. Hospitalizations in ICU during observation period: patients' distribution

The table will provide:

- distribution of patients by number of hospitalization in ICU during observation period (see 'Computed variables' chapter);
- descriptive statistics (mean, median, standard deviation, quartiles, min, max) of number of hospitalization in ICU during observation period per patient (see 'Computed variables' chapter);
- distribution of patients by "Type of admission" ([F10_RESOURCE_CONS. RES_Hosp_matrix_1__Inw - RES_Hosp_matrix_10__Inw]), considering only hospitalization in ICU according to the field [RES_Hosp_matrix_x__ICU_YN];

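### Objective #3: resource counts are not put on an annual scale, the protocol's cost analysis is missing from the SAP, and Tables 34–35 use the wrong denominator

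*SAP*

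**What the plan says.** **Protocol 9.7, secondary objective #3.** The annual scale is stated twice: "The annual direct health care resource consumption and related cost will be provided by means of descriptive statistics of the variables mentioned above", and again "Descriptive statistics (mean, standard deviation, median, minimum and maximum) of the annual direct health care resource consumption and related cost will be provided". Step (i) of the method says that consumption "will be computed during observational period in terms of pharmacological and non-pharmacological treatments". For cost, the protocol specifies valuation by outpatient tariff, DRG tariff and consumer price in 2015 euros, and adjustment for follow-up: "A monthly (or yearly) cost will be provided by taking into account patients according to duration of observation", by "parametrizing each patient to the 12-month observation period". It adds "Non-parametric bootstrap method will be applied to cost data for calculating 95% confidence intervals" and "A multiple linear regression model will be performed to investigate statistical significance of INHS cost predictors".

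**SAP.** Section 2.1 admits a patient to the FAS on eligibility and one TSQM-9 domain score at enrolment; no follow-up visit is required. Section 3 defines hospitalisations, hospital days, ER accesses, specialist and GP visits and laboratory tests as sums over the 6-month, 12-month and End-of-observation forms. Section 4.10 then says for Tables 20, 22, 24 and 26–28: "Descriptives and percentages will be computed out of the total number of FAS patients". Cost appears in SAP section 1 (objective 3) and in Chart 1, where it is assigned to the FAS, but in none of Tables 1–46 and in no computed variable.

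Tables 34 and 35 show treatment classes ongoing at the 6- and 12-month visits. Section 3 defines that status by the date of the visit, while section 4.10 takes percentages over the whole FAS.

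**The concern.** There are three related problems.

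1. **Counts.** A patient followed for 6 months and one followed for 13 months contribute to the same mean with equal weight, and nothing in the tables shows how long each was observed. Such a mean cannot be read as use per year. Table 3 reports withdrawals but not time observed. Hospitalisations are counted as numbers of records, so a patient with no follow-up form could also be programmed as zero unless the SAP says otherwise.

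2. **Cost.** Half of objective #3 would go unreported with no decision visible in the SAP. Section 4.9 of the same document openly states and dates a different departure from Protocol 9.7, so the silence on cost stands out.

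3. **Tables 34–35.** A patient who never had the visit cannot have a treatment status at that visit, yet stays in the denominator. Tables 10–16 use patients evaluable at the time point.

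At stake is the answer to a secondary objective. The primary objective, TSQM-9 by visit, is not touched.

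**Working it through.** **The plan's own figures.** Protocol 9.5 assumes 5% to 20% drop-out from 400 patients: 400 × 0.95 = 380 and 400 × 0.80 = 320, as stated. That range also covers non-evaluable and off-treatment patients, so loss to follow-up within the FAS may be smaller. Neither document gives exit times; those used below are assumptions.

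**Counts.** Let d be the share of the FAS that leaves early. Assume exits spread evenly over 12 months (mean 6), a constant event rate, and completers seen at month 12. The ratio of the raw mean to the true annual mean is then:

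| Scenario | Formula | d = 5% | d = 10% | d = 20% |
|---|---|---|---|---|
| Data up to exit | [(1−d)·12 + d·6] / 12 | 0.975 | 0.950 | 0.900 |
| Last scheduled form only, no-form patients missing | [(1−d)·12 + (d/2)·6] / [12·(1−d/2)] | 0.987 | 0.974 | 0.944 |
| Last scheduled form only, no-form patients scored zero | [(1−d)·12 + (d/2)·6] / 12 | 0.9625 | 0.925 | 0.850 |

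In the second and third rows, half of the leavers exit before month 6 and have no form; the other half have 6 months of data. Worked example, first row, d = 20%: (9.6 + 1.2)/12 = 0.900.

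**Offset from late visits.** With data up to exit, the mean final-visit month T that cancels the shortfall solves (1−d)·T + 6d = 12, so T = (12 − 6d)/(1 − d). This gives 12.32, 12.67 and 13.50 months for d = 5%, 10% and 20%. Completers seen at month 11 or 13 contribute 11/12 = 0.917 or 13/12 = 1.083 of a year, so even their raw counts are not exactly annual.

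**Cost, element by element.**

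| Protocol 9.7 | SAP |
|---|---|
| Tariff, DRG and consumer-price valuation | No cost variable in section 3 |
| Scaling to 12 months | None |
| Bootstrap 95% CI | None |
| Regression of cost predictors | None |
| Descriptive cost statistics | No cost table among Tables 1–46 |
| Cost as part of objective #3 | Kept in section 1 and Chart 1 |

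The table layouts (section 5) and the text of section 4.14 are not available, but every table title is visible and none concerns cost. The checks in SAP section 6 contain no cost item, and the revision history in section 7 does not mention cost.

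**Tables 34–35.** Let a be the share of the FAS without the visit. The reported share is (share among attenders) × (1 − a). A class used by 50% of attenders is reported as 47.5%, 45.0% or 40.0% for a = 5%, 10% or 20%. This takes the rule in section 3 as laid out in two bullets, so that a start date before the visit is always required. The brackets are unbalanced; under a looser reading, a patient without the visit could count as treated through the branch for therapy ongoing at the end of observation. The whole FAS is an unsuitable denominator under either reading.

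**The case against.** **Counts.** The explicit 12-month scaling sentence is worded for cost, and step (i) speaks of the observation period. The SAP does not label its counts annual, and Table 1 shows how many patients are evaluable at 6 and 12 months. This stands to the extent that, for consumption, the promise rests on the word *annual*. But the protocol attaches that word to consumption twice, and Table 1 gives no observation time. Using the FAS is not itself the fault: the protocol analyses lost patients up to their last visit, which is why time has to be accounted for.

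**Size.** The larger shortfalls assume that leavers have no End-of-observation form, or that missing forms are scored zero. The latter runs against SAP section 4, which excludes patients with missing data. That is fair, and the 2.5–10% range does not need those assumptions. The section 4 rule does nothing for partial follow-up. Net direction and size are unknown until visit timing is known.

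**Tables 34–35.** Chart 1 assigns ongoing treatments to the FAS, and the protocol does not ask for class shares at 6 and 12 months. Section 4 might also be read as excluding patients with no visit date. But section 4.10 names the whole FAS, so the two rules at least need reconciling.

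**Cost.** A reason may lie in the June 2017 meeting minutes or the September 2016 conference call that the SAP cites. Neither is available. Even so, the SAP still lists cost as an objective and as a planned analysis, and so contradicts itself.

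**Remedy.** Events per patient-year with a confidence interval go beyond what the protocol asks for counts. That is true; they are proposed because per-patient scaling is unstable for very short observation.

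**Conclusion.** The concern holds in all three parts and should be fixed. The missing cost analysis is the strongest part and needs no assumption: it is specified in the protocol, retained in the SAP's objectives and Chart 1, and has no planned output or stated reason. The count tables do not deliver annual consumption. With a constant event rate, even exits and data up to exit, raw means are 2.5%, 5% or 10% low at 5%, 10% or 20% attrition. If leavers supply only their last scheduled form, they are 1.3%, 2.6% or 5.6% low with no-form patients missing, and 3.8%, 7.5% or 15% low with them scored zero. These are illustrations: true FAS attrition may be below the protocol's range, and late final visits can cancel the shortfall. In Tables 34–35, on the natural reading of the rule, shares shrink in proportion to the patients without the visit.

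**What to change.** **Tables 20, 22, 24 and 26–28.** Keep the raw counts. For FAS patients with any post-baseline observation, add observation time (enrolment to last visit or exit) and per-patient counts and hospital days scaled to 12 months, with mean, SD, median, minimum and maximum. Because one event in one month scales to 12 a year, also give total events per patient-year with a 95% CI; a patient-level bootstrap, already named in the protocol for cost, is one option. State that patients with no follow-up form are missing, not zero, and footnote Chart 1 accordingly. Say in the report that time adjustment does not remove bias if event rates change before exit.

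**Cost.** Restore the protocol's analysis: valuation, scaling to 12 months, bootstrap CI and cost-predictor regression. If it was deliberately dropped, record a dated departure with the reason and delete cost from SAP section 1 and Chart 1; objective #3 then stays half unanswered.

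**Tables 34–35.** Use as denominator the FAS patients with a recorded date for that visit, and bracket the rule so that a start before the visit date always applies.

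**Price.** Time-adjusted use and Tables 34–35 need SAP wording and modest programming; enrolment and follow-up visit dates are already SAP fields. No exit date is named in the SAP text available, so it must be located in the eCRF or the last visit date used. Restoring cost is more work: unit costs must be assigned, and the hospitalisation fields the SAP names (ICU, type, duration, reason) include no DRG. Recording its removal takes one paragraph and two deletions.

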The **total number of days of hospitalization in ICU for each patient** will be the sum of the fields "Overall duration of admission (days)" [F10_RESOURCE_CONS. RES_Hosp_matrix_1_Adm - RES_Hosp_matrix_10_Adm], considering only the records referred to hospitalizations in ICU (see above) at the 6- and 12-month follow-up visits and the End of observation visit.

ER accesses for COPD, COPD exacerbations or COPD related adverse events during observation period

The **total number of ER accesses for each patient** will be the sum of the fields “N° ER accesses” [F10_RESOURCE_CONS.RES_ER_matrix_1_n_acc - RES_ER_matrix_12_n_acc] considering the 6- and 12-month follow-up visits and the End of observation visit.

Specialist outpatient visits for COPD, COPD exacerbations or COPD related adverse events during observation period
Patients with at least one specialist outpatient visit will be those with “Did the patient have any specialist outpatient visit for COPD, COPD exacerbations or COPD-related adverse events since the previous visit?” [F10_RESOURCE_CONS.RES_OUTP_YN] = “Yes” at 6-month follow-up visit OR at 12-month follow-up visits OR at End of observation visit.

The **total number of specialist outpatient visits per patient during observation period** will be computed as the sum of the field “Nr Visits” [F10_RESOURCE_CONS.RES_Nr_Visits], considering the 6- and 12-month follow-up visits and the End of observation visit.

General practitioner visits for COPD, COPD exacerbations or COPD related adverse events during observation period

The **total number of general practitioner visits per patient during observation period** will be computed as the sum of the field “N° of office visits (...)” [F10_RESOURCE_CONS.RES_GP_Visit_YN_Num], considering the 6- and 12-month follow-up visits and the End of observation visit.

Laboratory test for COPD, COPD exacerbations or COPD related adverse events during observation period

The **total number of laboratory test per patient during observation period** will be computed as the sum of the fields “N° of tests” [F10_RESOURCE_CONS.RES_Lab_matrix_1_num - RES_Lab_matrix_20_num] for each row of the matrix LABORATORY TESTS/EXAMINATIONS, considering the 6- and 12-month follow-up visits and the End of observation visit.

Patients with oxygen therapy during the observational period

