- descriptive statistics (mean, median, standard deviation, quartiles, min, max) of total number of days of hospitalization in ICU (see 'Computed variables' chapter);
- distribution of patients by reasons for hospitalization in ICU (i.e. "Hospitalization for" [F10_RESOURCE_CONS. RES_Hosp_matrix_1__hos_for - RES_Hosp_matrix_10__hos_for]).

Descriptives and percentages will be computed out of the total number of FAS patients.

Table 23. Hospitalizations in ICU during observation period: details

The table will provide:

- distribution of hospitalizations in ICU by "Type of admission" ([F10_RESOURCE_CONS. RES_Hosp_matrix_1__Inw - RES_Hosp_matrix_10__Inw]), considering only hospitalization in ICU according to the field [RES_Hosp_matrix_x__ICU_YN];
- distribution of hospitalizations in ICU by reasons for hospitalization (i.e. "Hospitalization for" [F10_RESOURCE_CONS. RES_Hosp_matrix_1__hos_for - RES_Hosp_matrix_10__hos_for]).

Statistics will be computed out of the total number of hospitalizations in ICU during observation period in FAS patients.

Table 24. Emergency room accesses: patients' distribution

The table will provide:

- distribution of patients by number of ER accesses during observation period per patient (see 'Computed variables' chapter);

- descriptive statistics (mean, median, standard deviation, quartiles, min, max) of number of ER accesses during observation period per patient (see 'Computed variables' chapter);
- distribution of patients by reasons of ER admission (i.e. "Admission for" [F10_RESOURCE_CONS.RES_ER_matrix_1_adm_for - RES_ER_matrix_12_adm_for]).

Descriptives and percentages will be computed out of the total number of FAS patients.

Table 25. Emergency room accesses: details

The table will provide:

- distribution of reasons of ER accesses during observation period (i.e. "Admission for" [F10_RESOURCE_CONS.RES_ER_matrix_1_adm_for - RES_ER_matrix_12_adm_for]).

Statistics computed over the total number of ER accesses during observation period in FAS patients.

Table 26. Specialist outpatient visits: patients' distribution

The table will provide:

- descriptive statistics (mean, median, standard deviation, quartiles, min, max) of the total number of specialist outpatient visits per patient during observation period (see 'Computed variables' chapter);
- distribution of patients by number of specialist outpatient visits per patient during observation period (see 'Computed variables' chapter);

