- distribution of patients by type of specialist outpatient visits performed during observation period (i.e. "Specialist" [F10_RESOURCE_CONS.Specialist]);
- distribution of patients by reasons of specialist outpatient visit (i.e. "Visit for" [F10_RESOURCE_CONS.RES_Visit_for]).

Descriptives and percentages will be computed out of the total number of FAS patients.

Table 27. General practitioner visits: patients' distribution

The table will provide:

- distribution of patients by total number of general practitioner visits per patient during observation period (see 'Computed variables' chapter);
- descriptive statistics (mean, median, standard deviation, quartiles, min, max) of the total number of general practitioner visits per patient during observation period (see 'Computed variables' chapter).

Descriptives and percentages will be computed out of the total number of FAS patients.

Table 28. Laboratory tests: patients' distribution

The table will provide:

- distribution of patients by total number of laboratory test per patient during observation period (see 'Computed variables' chapter);
- descriptive statistics (mean, median, standard deviation, quartiles, min, max) of total number of laboratory test per patient during observation period (see 'Computed variables' chapter);
- distribution of patients by type of test/examination during observation period (i.e. "Test/examination" [F10_RESOURCE_CONS.RES_Lab_matrix_1_Test - RES_Lab_matrix_20_Test]);
- distribution of patients by reasons of test/examination (i.e. "Test/examination for" [F10_RESOURCE_CONS.RES_Lab_matrix_1_for - RES_Lab_matrix_20_for]).

Descriptives and percentages will be computed out of the total number of FAS patients.

Table 29. Laboratory tests: details

The table will provide:

- frequency of each type of test/examination during observation period (listed in field "Test/examination" [F10_RESOURCE_CONS.RES_Lab_matrix_1_Test - RES_Lab_matrix_10_Test] and according to the number of tests recorded in field "N° of tests" [F10_RESOURCE_CONS.RES_Lab_matrix_1_num - RES_Lab_matrix_20_num]),
- distribution of reasons of test/examination (i.e. "Test/examination for" [F10_RESOURCE_CONS.RES_Lab_matrix_1_for - RES_Lab_matrix_20_for]).

Statistics computed over the total number of Laboratory tests during observation period in FAS patients.

Table 30. Oxygen therapy

The table will provide:

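### SAP Table 29 reads test type from rows 1–10 but the number of tests from rows 1–20; Table 25 and the reasons line of Table 29 do not state the weighting by row count

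*SAP*

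**What the plan says.** The laboratory form is a matrix of up to 20 rows. Each row carries a test, a number of tests and a reason. SAP section 3 defines a patient's number of laboratory tests as the sum of the number-of-tests fields over rows 1 to 20, across the 6-month, 12-month and end-of-observation visits. ER accesses are likewise a sum of per-row counts, over the 12 fields "RES_ER_matrix_1_n_acc - RES_ER_matrix_12_n_acc". One row can therefore stand for several tests or several accesses.

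Section 4.10 uses these fields as follows.

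- **Table 28** (patients) takes test type from rows 1 to 20, with FAS patients as denominator.
- **Table 29, type line** takes the frequency of each test type from "RES_Lab_matrix_1_Test - RES_Lab_matrix_10_Test] and according to the number of tests recorded in field", and then cites the number-of-tests fields for rows 1 to 20.
- **Table 29, reasons line** takes the reason from "RES_Lab_matrix_1_for - RES_Lab_matrix_20_for" and says nothing about the number of tests in the row.
- **Table 29, denominator**: "Statistics computed over the total number of Laboratory tests during observation period in FAS patients".
- **Table 25** gives the "distribution of reasons of ER accesses during observation period", read from the 12 row-level admission-reason fields. Its denominator is given as "Statistics computed over the total number of ER accesses during observation period in FAS patients". It does not mention the access count of the row.

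**The concern.** The type line of Table 29 contradicts itself on the row range. It also conflicts with Table 28 and with the section 3 total over which it is computed. A programmer who follows the text would give tests in rows 11 to 20 a count but no type. Among the tables described in section 4.10, Table 29 is the only one that counts tests, rather than patients, by type, so no other table would supply the missing figures.

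The reason lines raise a different problem. The denominator counts events, the reason is recorded once per row, and the text does not say how the two are joined. Two programmers could produce different percentages from the same data.

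**Working it through.** The plan gives no figure to reproduce here. The check sets the field ranges side by side and then works out how large a shortfall could be.

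**1. Row ranges for laboratory tests**

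| Place in the SAP | Type field | Number-of-tests field | Reason field |
|---|---|---|---|
| Section 3, total tests | not used | rows 1–20 | not used |
| Table 28 | rows 1–20 | through the section 3 total | rows 1–20 |
| Table 29, type line | **rows 1–10** | rows 1–20 | not used |
| Table 29, reasons line | not used | not mentioned | rows 1–20 |

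Only one entry is out of line. Because Table 28 cites `RES_Lab_matrix_20_Test`, the form does hold type fields for rows 11 to 20. The short range is not a limit of the form.

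**2. Size of the range error**

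The share of tests lost from the type line is the number of tests in rows 11–20 divided by all tests. The documents give neither quantity. For a single form with m filled rows and equal counts per row (an assumption), the share that keeps a type is 100 × min(m, 10)/m:

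| Filled rows m | Share with a type |
|---|---|
| up to 10 | 100% |
| 11 | 10/11 = 90.9% |
| 12 | 10/12 = 83.3% |
| 15 | 10/15 = 66.7% |
| 20 | 10/20 = 50.0% |

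These are shares for one such form. Pooled over all forms the loss is diluted by every form with 10 or fewer filled rows, and it is zero if no form exceeds 10. A test type entered only in rows 11–20 would appear in Table 28 and be absent from Table 29.

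**3. Reason lines if rows were counted without weights**

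Let k be the mean number of events per filled row. Rows divided by events is 1/k, so unweighted reason percentages would sum to 100/k %. The documents do not give k. Over an assumed range of 1 to 3:

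| k | Sum of percentages |
|---|---|
| 1 | 100% |
| 1.1 | 90.9% |
| 1.25 | 80.0% |
| 1.5 | 66.7% |
| 2 | 50.0% |
| 3 | 33.3% |

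**4. Example with assumed ER rows**

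Take four rows: COPD with 2 accesses, exacerbation with 3, exacerbation with 1, adverse event with 1. The total is 2 + 3 + 1 + 1 = 7 accesses.

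| Reason | Weighted by accesses | Rows over accesses |
|---|---|---|
| COPD | 2/7 = 28.6% | 1/7 = 14.3% |
| Exacerbation | 4/7 = 57.1% | 2/7 = 28.6% |
| Adverse event | 1/7 = 14.3% | 1/7 = 14.3% |
| Sum | 7/7 = 100% | 4/7 = 57.1% |

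Rescaling the unweighted column to 100% does not repair it: adverse events become 1/4 = 25%, against 14.3% of accesses. With weighting, and with the type range extended to row 20, each distribution sums to 100% provided that no type or reason is missing.

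**The case against.** The strongest reply is that the range is a typing slip in one line of a secondary descriptive table, and that nothing else in the text is actually wrong. Much of this stands.

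- A reader might infer that Tables 25 and 29 divide counts of rows by counts of events. The SAP does not say so. The type line of Table 29 is explicitly weighted ("and according to the number of tests recorded in field"). For Table 25 and the reasons line, row counting would be an inference from silence. Where section 3 wants rows or records counted, as for exacerbations, hospitalizations and therapies, it says so. A distribution of reasons over total accesses can fairly be read as access-weighted. What remains is that Table 29 states the weighting in one line and omits it in the next, which leaves an unweighted reading open.
- A reader might also infer that the percentages will fail to sum to 100%. That needs multi-event rows left unweighted, or more than 10 filled test rows. The documents give the frequency of neither.
- Nor do the documents support a general disagreement with Tables 24 and 28. Those tables give percentages of patients, and they need not match percentages of events.
- Section 6 omits Tables 25 and 29 from the tables to be reprogrammed or independently verified. It does, however, have every table verified by a biostatistician and reviewed for consistency, so it cannot be said that the problem would pass unnoticed.
- The table layouts of section 5 are not visible in the text reviewed and may fix the counting unit.

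None of this removes the range conflict. A slip in a field range is still the rule that a programmer is told to apply, and a later consistency review does not make that rule right.

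**Conclusion.** The point holds in two parts of unequal weight.

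First, the type range in Table 29 is a wrong analysis rule. It conflicts with the count range in its own line, with Table 28 and with the total that serves as its denominator. Type frequencies are understated whenever a form has more than 10 filled test rows. How often that happens is unknown, so the effect on the table may be nil or material.

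Second, the weighting of reasons in Table 25 and in the second line of Table 29 is unstated. This is under-specification, not a stated wrong ratio. It matters only if some rows hold more than one event and the programmer counts rows.

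The impact is confined to descriptive tables for secondary objective #3. Per-patient totals in Tables 24 and 28 and the correlations in Table 37 rest on the section 3 sums and are unaffected, as is the primary objective. The percentages in the working rest on assumed rows per form and events per row; they show a range and do not predict the study's results.

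**What to change.** 1. In the type line of Table 29, change the range to `RES_Lab_matrix_1_Test` to `RES_Lab_matrix_20_Test`.
2. In the reasons line of Table 29, state that each row's reason is weighted by that row's number of tests, as the type line already does.
3. In Table 25, state that each row's reason is weighted by that row's number of ER accesses.
4. Confirm that the section 5 layouts and the programs for both tables use the same counting unit.

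The cost is three short wording changes in the SAP and the matching lines of code. No new data are needed and no other analysis changes.
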